To test the efficacy of the PSB intervention in reducing stress, alcohol craving and use, all analyses will be conducted using the intent-to-treat sample and each hypothesis will be tested using General Linear models (GLMs) (Diggle, Heagerty, Liang, & Zeger, 2002) examining the main effects of Time (pre-/post-/Follow-up).

For smartphone data, alcohol use outcomes obtained from mobile app will be defined in both dichotomous and continuous manner (e.g., time to first drink or time to heavy drinking after the prevention; percent days abstinence and heavy drinking days (men: 5 or more; women: 4 or more) as continuous measures). Frequency, the total number of days of stress or alcohol use; and quantity, the average amount of alcohol use (number of drinks) or average levels of stress per occasion will also be computed. Multiple regression and mixed effects regression models (MRMs) will be used to evaluate the effects of prevention on prospective repeated assessments of stress, emotion, alcohol use, craving, and mood related data. Specific MRMs will model within person time varying and invariant data from daily stress and substance use patterns to assess group differences and examine whether behavioral changes after prevention predicts future stress and alcohol-related behaviors.

SECTION II: RESEARCH INVOLVING DRUGS, BIOLOGICS, RADIOTRACERS, PLACEBOS AND DEVICES

If this section (or one of its parts, A or B) is not applicable, check off N/A and delete the rest of the section.

A. RADIOTRACERS N/A

B. DRUGS/BIOLOGICS N/A

B. DEVICES N/A

SECTION III: RECRUITMENT/CONSENT AND ASSENT PROCEDURES

1. Targeted Enrollment: Give the number of subjects:

- Targeted for enrollment at Yale for this protocol: 100
- If this is a multi-site study, give the total number of subjects targeted across all sites: n/a

2. Indicate recruitment methods below. Attach copies of any recruitment materials that will be used.

 Flyers	 Internet/web postings	 Radio
 Posters	 Mass email solicitation	 Telephone
 Letter	 Departmental/Center website	 Television
 Medical record review*	 Departmental/Center research boards	 Newspaper
 Departmental/Center newsletters	 Web-based clinical trial registries	 Clinicaltrials.gov
 YCCI Recruitment database	 Social Media (Twitter/Facebook):	
 Other:		

* Requests for medical records should be made through JDAT as described at
<http://medicine.yale.edu/ycci/oncore/availableservices/datarequests/datarequests.aspx>

3. Recruitment Procedures:

- Describe how potential subjects will be identified. *Write here*

Subjects will be recruited through flyers posted in the community, and advertisements on social media/internet sites. Potential subjects will complete an initial telephone screening or be asked to complete a Qualtrics prescreening survey and then will be scheduled to meet with research staff to complete an intake appointment at the Yale Stress Center.

For the COVID study, participants with COVID-19 stress, Participants will also be recruited from the regions that are most significantly affected by COVID-19 in the US (based on the Center for Disease Control and Prevention (CDC), www.cdc.gov) in addition to Connecticut area by placing targeted advertisements on social networking outlets (e.g., Craigslist, Facebook, and Twitter) or other local platforms.

b. Recruitment of participants will also be conducted through a dedicated Yale Stress Center (YSC) Recruitment Channel specializing in coordinating centralized recruitment of participants into center studies. This recruitment team that has a well-developed treatment referral network comprising a variety of treatment, social service and addiction referral sources in the Greater New Haven area.

The YSC Recruitment Team provides coordinated centralized recruitment of participants into YSC affiliated studies typically through the placement of weekly advertisements in area newspapers, posting flyers in local areas. In addition, referrals from the Yale Substance Abuse Treatment facilities will also be a source of patients for study participation. Staff at these facilities will be given flyers detailing the study and encouraged to have their clients contact us for screening. This approach has allowed us to recruit subjects from a variety of race and socioeconomic backgrounds. Describe how potential subjects are contacted.

Potential subjects will contact us via our toll-free phone number, which can be obtained from the study advertisements on social media/internet sites, or flyers posted in the community, and be screened by research staff.

c. Who is recruiting potential subjects? Research staff at the Yale Stress Center

4. Assessment of Current Health Provider Relationship for HIPAA Consideration:

Does the Investigator or any member of the research team have a direct existing clinical relationship with any potential subject?

Yes, all subjects
 Yes, some of the subjects
 No

If yes, describe the nature of this relationship. *Write here*

5. Request for waiver of HIPAA authorization: (When requesting a waiver of HIPAA Authorization for either the entire study, or for recruitment purposes only. Note: if you are collecting PHI as part of a phone or email screen, you must request a HIPAA waiver for recruitment purposes.)

Choose one:

For entire study
 For recruitment/screening purposes only
 For inclusion of non-English speaking subject if short form is being used and there is no translated HIPAA research authorization form available on the University's HIPAA website at hipaa.yale.edu.

- i. Describe why it would be impracticable to obtain the subject's authorization for use/disclosure of this data:
- ii. If requesting a waiver of **signed** authorization, describe why it would be impracticable to obtain the subject's signed authorization for use/disclosure of this data:

The investigator assures that the protected health information for which a Waiver of Authorization has been requested will not be reused or disclosed to any person or entity other than those listed in this application, except as required by law, for authorized oversight of this research study, or as specifically approved for use in another study by an IRB.

Researchers are reminded that unauthorized disclosures of PHI to individuals outside of the Yale HIPAA-Covered entity must be accounted for in the “accounting for disclosures log”, by subject name, purpose, date, recipients, and a description of information provided. Logs are to be forwarded to the Deputy HIPAA Privacy Officer.

6. Process of Consent/Accent: Describe the setting and conditions under which consent/assent will be obtained, including parental permission or surrogate permission and the steps taken to ensure subjects' independent decision-making.

Following the initial telephone screening, eligible participants will meet with a research assistant to obtain informed consent. The consent process can be done either in person or remotely via a REDCap eConsent if needed. The following procedure will be implemented for the eConsent procedure.

First, the potential participants will receive a secure REDCap link to view the consent form and have a remote session with research staff. After reviewing the consent form, they will go over the study procedure and all aspects of the consent form with staff and have enough time for study Q & A and the risk involved before making decisions. If they agree to participate, they will be asked to sign their name using a mouse on an eConsent form. Then, they will select “Next Page” at the bottom and a read only copy of the consent will be generated that they can review, download, and/or print. Also, at the bottom of the page they will view “I certify that all the information in the document above is correct, and I understand that signing this form electronically is the equivalent of signing a physical document.” Once this is selected, they will be able to submit the consent form. The completed PDFs will be downloaded and stored in a study folder that can only be accessed with a unique password in a 3-lock Yale ITS managed storage. The e-consent also records the IP address of the participant and displays this information in the file repository in order to help regulate potential duplicate forms from a single IP address.

7. Evaluation of Subject(s) Capacity to Provide Informed Consent/Accent: Indicate how the personnel obtaining consent will assess the potential subject's ability and capacity to consent to the research being proposed.

After the participant has read over the consent form, research staff will further explain the study, including the risks involved. Research staff will ask the potential subject how well they understood the consent, and answer questions they may have.

8. Non-English Speaking Subjects: Explain provisions in place to ensure comprehension for research involving non-English speaking subjects. If enrollment of these subjects is anticipated, translated copies of all consent materials must be submitted for approval prior to use.

Non-English speaking individuals will not be recruited for this study.

As a limited alternative to the above requirement, will you use the short form* for consenting process if you unexpectedly encounter a non-English speaking individual interested in study participation and the translation of the long form is not possible prior to intended enrollment? YES NO

Note* If more than 2 study participants are enrolled using a short form translated into the same language, then the full consent form should be translated into that language for use the next time a subject speaking that language is to be enrolled.

Several translated short form templates are available on the HRPP website (yale.edu/hrpp) and translated HIPAA Research Authorization Forms are available on the HIPAA website (hipaa.yale.edu). If the translation of the short form is not available on our website, then the translated short form needs to be submitted to the IRB office for approval via modification prior to enrolling the subject. *Please review the guidance and presentation on use of the short form available on the HRPP website.*

If using a short form without a translated HIPAA Research Authorization Form, please request a HIPAA waiver in the section above.

9. **Consent Waiver:** In certain circumstances, the HIC may grant a waiver of signed consent, or a full waiver of consent, depending on the study. If you will request either a waiver of consent, or a waiver of signed consent for this study, complete the appropriate section below.

Not Requesting any consent waivers

Requesting a waiver of signed consent:

- Recruitment/Screening only** (if for recruitment, the questions in the box below will apply to recruitment activities only) telephone screen
- Entire Study** (Note that an information sheet may be required.)

For a waiver of signed consent, address the following:

- Would the signed consent form be the only record linking the subject and the research? YES NO
- Does a breach of confidentiality constitute the principal risk to subjects? YES NO

OR

- Does the research pose greater than minimal risk? YES NO
- Does the research include any activities that would require signed consent in a non-research context? YES NO

Requesting a waiver of consent:

- Recruitment/Screening only** (if for recruitment, the questions in the box below will apply to recruitment activities only)
- Entire Study**

For a full waiver of consent, please address all of the following:

- Does the research pose greater than minimal risk to subjects?
 Yes *If you answered yes, stop. A waiver cannot be granted.*
 No
- Will the waiver adversely affect subjects' rights and welfare? YES NO
- Why would the research be impracticable to conduct without the waiver? *Write here*
- Where appropriate, how will pertinent information be returned to, or shared with subjects at a later date?
Write here

SECTION IV: PROTECTION OF RESEARCH SUBJECTS

Confidentiality & Security of Data:

1. What protected health information (medical information along with the HIPAA identifiers) about subjects will be collected and used for the research?

Results of the psychological assessments, self-reports, and data collected during pre-intervention, post-intervention, and interventions, will be collected and used for research. The proposed study will be conducted by specialized and trained research staff using standardized and psychosocial assessments. Data collected and analyzed in the study will be derived from two main sources: semi-structured clinical interviews and self-rating scales: psychiatric history, medical history, demographic self-reports of age, race, socioeconomic status, marital status, educational and occupational levels.

2. How will the research data be collected, recorded and stored?

Research data will be collected on paper assessments and using Yale University's REDCap system. All research data is stored in two places--one as a hardcopy in a locked file, with records identified only by the participant's study number, and the second in computerized databases protected by two-level password systems on Yale encrypted desktop computers.

3. How will the digital data be stored? CD DVD Flash Drive Portable Hard Drive Secured Server
 Laptop Computer Desktop Computer Other
4. What methods and procedures will be used to safeguard the confidentiality and security of the identifiable study data and the storage media indicated above during and after the subject's participation in the study?

Upon enrollment, all study subjects will be assigned a unique study number. The study number—and no personal identifiers—will be used as labels for study records, samples and any other related research documentation. All electronic and digital files will be stored on the secure Yale network, and the PC accessing the network will be password protected and encrypted. All paper files, such as consent forms, will be stored in a locked file cabinet in a locked office and access is limited to members of the study research team.

All portable devices must contain encryption software, per University Policy 5100. If there is a technical reason a device cannot be encrypted please submit an exception request to the Information Security, Policy and Compliance Office by clicking on url <http://its.yale.edu/egrc> or email [contact]

5. What will be done with the data when the research is completed? Are there plans to destroy the identifiable data? If yes, describe how, by whom and when identifiers will be destroyed. If no, describe how the data and/or identifiers will be secured.

Upon completion of study and data analysis, a professional information protection, storage, and disposal company will be retained to dispose of research files and informed consent documentation.

6. If appropriate, has a Certificate of Confidentiality been obtained? Yes, we obtained CoC.

SECTION V: POTENTIAL BENEFITS

Potential Benefits: Identify any benefits that may be reasonably expected to result from the research, either to the subject(s) or to society at large. (Payment of subjects is not considered a benefit in this context of the risk benefit assessment.)

There are some potential benefits of the proposed study. First, monitoring drinking, learning stress reduction and breathing modulation may be helpful to some subjects. Second, this study will evaluate the PSB as a potential alcoholism prevention program. If the efficacy of the PSB intervention is supported, our findings will identify an effective prevention strategy that can be delivered in the participants' community. Given these valuable benefits to the subjects and their community and the minimal risks of the study procedures, we believe that the study risks are reasonable in relation to the potential benefits.

Also, stress reduction and breathing methods may help participants self-regulate distress and emotion without over-reactivity. Thus, these skills may then allow participants to be particularly effective in implementing knowledge about regulating craving and drinking urge and to adopt healthier choices and habits.

SECTION VI: RESEARCH ALTERNATIVES AND ECONOMIC CONSIDERATIONS

1. **Alternatives:** What other alternatives are available to the study subjects outside of the research? Subjects need not participate in this study to receive stress management or breathing training or substance use counseling.

Payments for Participation (Economic Considerations): Describe any payments that will be made to subjects, the amount and schedule of payments, and the conditions for receiving this compensation.

For the 4-week intervention: participants will be compensated for their time taken for a series of study appointments and participations over the course of 2.5 months of the study period. The total amount that each participant may receive is up to \$778 per participant for completing all aspects of the study (baseline assessments, 4-week digital interventions, 28-day daily monitoring, and a follow-up evaluation at the end of 30 days).

Baseline Assessments: Participants in the assessment and intervention groups will be paid up to \$100 for screening, DSM-5 diagnosis, & 4-5 online baseline assessments (\$20 per session).

4-week Period:

Intervention group

Participant will receive up to \$488 for completing the study procedure related to 4-week intervention for treatment sessions, smartphone app surveys and post-treatment evaluation.

Sessions: Participants will receive up to \$200 including \$20 for per session (two sessions weekly; 8 sessions in total ($8 \times \$20 = \160) and bonus. An additional \$20 bonus will be rewarded for the completion of all 4 sessions every 2 weeks of treatment during the 4-week treatment period.

Smartphone surveys: They will also receive up to \$248 for the completion of a 28-day daily smartphone app surveys including \$3 for each daily intervention exercise ($28 \times \$3 = \84), smartphone monitoring survey ($28 \times \$3 = \84), and weekly bonus. They will receive an additional weekly bonus of \$20 for completing 100% (14/14 surveys; submitted a total number of two surveys (daily evening surveys + daily intervention exercise) per week), \$18 for completing at least 92.5% (13/14 surveys; submitted a total number of two surveys (daily evening surveys + daily intervention exercise) per week) or \$16 for completing at least 86% (12/14 surveys; submitted a total number of two surveys (daily evening surveys + daily intervention exercise) per week) of the surveys in each week. Both the daily evening survey and daily intervention exercise must be completed for a day to count towards the weekly bonus.

At the end of treatment, they will also receive \$40 for a post assessment at the end of 4-week intervention.

Follow-up evaluations: Participant will be compensated for their time up to \$190 for 30-days follow-up after treatment. For daily monitoring follow-up assessments, they will be paid \$3 for daily survey over 30 days ($30 \times \$3 = \90). They will also receive additional \$20 biweekly bonus for completing at least 100% (14 out of 14 surveys), \$15 for 90% (13 out of 14 surveys), and \$10 for 80% (12 out of 14 surveys) of every 14-day survey. Additionally, they will also receive \$60 for a video session and completing online evaluation assessments at the end of the 30-day follow-up period.

Therefore, the total that the intervention group may be reimbursed for their time if they complete the study, attend all 8 treatment sessions and a 100% completion rate for the smartphone surveys, is \$778.

- 2. Costs for Participation (Economic Considerations):** Clearly describe the subject's costs associated with participation in the research, and the interventions or procedures of the study that will be provided at no cost to subjects.

All parts of the research process will be provided at no cost to the subjects.

- 3. In Case of Injury:** This section is required for any research involving more than minimal risk, and for minimal risk research that presents the potential for physical harm (e.g., research involving blood draws).

While medical therapy will be offered for any physical injuries sustained as a consequence of participation in this research, the subject and their insurance carrier will be responsible for the cost of such treatment. Financial compensation for injury is not available.

- a. Will medical treatment be available if research-related injury occurs? Medical therapy will be offered for any physical injuries sustained as a consequence of participation in this research.
- b. Where and from whom may treatment be obtained? Any licensed facility / practitioner
- c. Are there any limits to the treatment being provided? *No*
- d. Who will pay for this treatment? The subject and their insurance carrier will be responsible for the cost of treatment. Financial compensation for injury is not available.
- e. How will the medical treatment be accessed by subjects? Subjects will be encouraged to receive services through practitioners in any licensed facility where their insurance company may cover their medical expenses.

IMPORTANT REMINDERS

Will this study have a billable service? **Yes** **No**

A billable service is defined as any service rendered to a study subject that, if he/she was not on a study, would normally generate a bill from either Yale-New Haven Hospital or Yale Medical Group to the patient or the patient's insurer. The service may or may not be performed by the research staff on your study, but may be provided by professionals within either Yale-New Haven Hospital or Yale Medical Group (examples include x-rays, MRIs, CT scans, specimens sent to central labs, or specimens sent to pathology). Notes: 1. There is no distinction made whether the service is paid for by the subject or their insurance (Standard of Care) or by the study's funding mechanism (Research Sponsored). 2. This generally includes new services or orders placed in EPIC for research subjects.

If answered, "yes", this study will need to be set up in OnCore, Yale's clinical research management system, for Epic to appropriately route research related charges. Please contact [contact]

Are there any procedures involved in this protocol that will be performed at YNHH or one of its affiliated entities?
Yes **No**

If Yes, please answer questions a through c and note instructions below.

- a. Does your YNHH privilege delineation currently include the **specific procedure** that you will perform? **Yes** **No**
- b. Will you be using any new equipment or equipment that you have not used in the past for this procedure? **Yes** **No**
- c. Will a novel approach using existing equipment be applied? **Yes** **No**

If you answered "no" to question 4a, or "yes" to question 4b or c, please contact the YNHH Department of Physician Services ([name]) for prior approval before commencing with your research protocol.

IMPORTANT REMINDER ABOUT RESEARCH AT YNHH

Please note that if this protocol includes Yale-New Haven Hospital patients, including patients at the HRU, the Principal Investigator and any co-investigators who are physicians or mid-level practitioners (includes PAs, APRNs, psychologists and speech pathologists) who may have direct patient contact with patients on YNHH premises must have medical staff appointment and appropriate clinical privileges at YNHH. If you are uncertain whether the study personnel meet the criteria, please telephone the Physician Services Department at [contact]. **By**

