DIGITAL INTERVENTIONS TO TREAT HAZARDOUS DRINKING

NCT04890652

PROTOCOL VERSION DATE 9/4/2022

HRP-503B – BIOMEDICAL RESEARCH PROTOCOL
(2017-1)

Protocol Title: Effects of Stress on Emotion and Risky Drinking

Principal Investigator: [name]

(If applicable) Clinicaltrials.gov Registration #: [Click or tap here to enter text.](#)

SECTION I: RESEARCH PLAN

1. Statement of Purpose:

Studies have shown that stress is a major contributor to stress-related clinical disorders and to substance use problems including alcoholism (Perkins, 1999; Sebena, El Ansari, Stock, Orosova, & Mikolajczyk, 2012). Stress response involves increased arousals in the autonomic nervous system (ANS) (Thayer, Ahs, Fredrikson, Sollers, & Wager, 2012). In particular, it is well documented that alcoholism is highly associated with stress and ANS disruption, suggesting that a strategy to address stress and ANS regulation may be helpful to reduce symptoms related to stress, mood, and addiction. For example, a breathing technique has shown to be effective in relieving stress-induced arousal. Studies have found that voluntarily regulated breathing practices normalize ANS system and improve sympatho-vagal balance, which resulted in reduction in psychiatric symptoms including anxiety, stressor-related symptoms, and addiction (Gerbarg & Brown, 2016). Relieving stress and arousal is particularly crucial in preventing alcohol addiction, as an inability to relax even during the neutrally relaxing state has been associated with high alcohol craving and early relapse in patients with alcoholism (Seo et al., 2013).

Overall purpose:

The current study will examine the effects of an intervention involving Problem-focused target intervention, Stress management, and Breathing modulation (PSB intervention) on improving symptoms of mood and addiction related symptoms including mood, craving, and addictive behaviors. The purpose of the 4-week intervention is to test the efficacy of the 4-week intervention consisting of 8 sessions for those who are willing to invest a month of their time towards improving their symptoms and subsequent follow-up.

The specific aims are as follows:

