Aim (4-week intervention): To examine the effects of the PSB intervention on mood and addiction related symptoms (emotional problems, craving, substance use) in individuals with either risky drinking problems or with high stress after the 4-week intervention (8 sessions) of two sessions per week. The effects will be examined before and after the 4- week intervention.

The effects of the 4-week intervention on daily mood, stress and substance use behaviors will also be examined during a 30 -day follow-up. Participants will be followed using a smartphone app to examine the effects of the PSB intervention on daily mood, stress and alcohol use behaviors in a real-life setting. And participant will receive an online evaluation assessment at the end of the 30-day follow-up period.

2. **Probable Duration of Project:** State the expected duration of the project, including all follow-up and data analysis activities.

Study (4-week intervention): 2.5 months

(2-3 weeks for 4-5 baseline intake sessions; 4 weeks for the telehealth intervention (8 session, twice weekly) with daily monitoring and intervention aids for assessing treatment progress via smartphone app survey; 1 post assessment; 30 days for daily follow-up via smartphone app; 1 post follow-up assessment)

3. **Background:** Describe the background information that led to the plan for this project. Provide references to support the expectation of obtaining useful scientific data.

Habitual alcohol abuse and stress-related mood disturbance are serious problems (Naimi et al., 2003; Wechsler et al., 2002). Studies have shown that stress is one of major contributors to mental health disorders including emotional disorders (e.g., depression, anxiety) or alcohol abuse problems (e.g., hazardous drinking) (Perkins, 1999; Sebena et al., 2012). Despite the significance of stress-related clinical disorders, challenges remain in implementing effective prevention and treatment approaches, as those with either high-risk drinking or high stress not only disregard their mood and substance-related problems, but also respond inadequately to currently available prevention or treatment programs.

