The COVID Stress Scales (CSS) (Taylor et al., 2020) is a 36-item designed to measure COVID-19 stress and anxiety symptoms including COVID danger and contamination fears, COVID fears about economic consequences, COVID xenophobia, COVID compulsive checking and reassurance seeking and COVID traumatic stress symptoms.

The Psychosocial Impact of COVID-19 (PIC) (Chung, 2020) is a 2-item assessing the level of difficulties and distress in people's lives over the past two weeks.

The Psychological Stress Associated with the COVID-19 Crisis questionnaire (PSACC) (M. Adamson, 2020) is a 37-item designed to measure the level of stress during the COVID-19 pandemic and characterize it according to location, gender, income, and other factor.

The UCLA Loneliness Scale (Version3) (Russell, 1996) is a 20-item measure that assesses how often a person feels disconnected from others.

The Interpersonal Support Evaluation List (ISEL) (Russell, 1996) is designed to measure perceptions of social support among individuals in the general population.

The COVID-19 Community Response Survey-Social Distancing Impacts (JHU-SDI) (Johns-Hopkins, 2020a) is designed to measure the impact of COVID-19 on people's lives due to a precautionary measure of social distancing.

The COVID-19 Community Response Survey-Substance Use (JHU-SU) (Johns-Hopkins, 2020b) is a 15-item designed to assess the use of substance after and during the COVID-19 pandemic.

(b) Target Intervention Combined with Breathing and Stress Management (PSB)

Subsequently, after the completion of the baseline assessment, all subjects will remotely participate in a 4-week digital intervention via video communications using platforms approved by Yale University IT services such as Zoom, Skype for Business, or Microsoft Teams. For 4 weeks, participants will attend 1.5 to 2 hours individual therapy sessions (8 sessions in total, twice a week) with [name] and her clinical team for prevention for alcohol use disorder using video communications. They will also be asked to use a smartphone app daily to assess treatment progress and learn coping skills (e.g., homework). At the end of the 4-week digital intervention, there will be post-treatment evaluations. Some components of the PSB intervention include:

- (1) Problem-focused target intervention partially adapted from cognitive behavioral therapy and NIAAA-approved coping skills training strategies (Kadden et al., 2003).

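### Section 13 tests the efficacy of PSB by the main effect of Time, but all subjects receive PSB and no comparator is defined, so a significant result shows change that cannot be attributed to PSB

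*Combined protocol and SAP*

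**What the plan says.** Section I, 13 (Statistical Considerations) states its goal as "To test the efficacy of the PSB intervention in reducing stress, alcohol craving and use". It pursues that goal in the intent-to-treat sample with general linear models "examining the main effects of Time (pre-/post-/Follow-up". No group term or Group x Time term is named for those models. For the smartphone data, multiple regression and mixed models "will be used to evaluate the effects of prevention on prospective repeated assessments of stress" and of the other daily outcomes. The mixed models are also to assess group differences, but the groups are not identified.

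Section I, 4(b) says that "all subjects will remotely participate in a 4-week digital intervention". The 100 subjects are not divided into arms in Section I, 4 or in Section III, 1.

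The same causal wording appears elsewhere:
- Section I, 1 says the purpose "is to test the efficacy of the 4-week intervention consisting of 8 sessions".
- The Aim is "To examine the effects of the PSB intervention on mood and addiction related symptoms", examined before and after the four weeks.
- For the follow-up, "The effects of the 4-week intervention on daily mood, stress and substance use behaviors will also be examined".
- The end of Section I, 3 (Background) again speaks of efficacy.
- Section V (Potential Benefits) says that, if efficacy is supported, the findings will identify an effective prevention strategy.

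**The concern.** A test of efficacy asks what PSB did beyond what would have happened without it. When every subject is treated and there is no control, waitlist, historical or external reference, the main effect of Time measures change from all causes together. Section 13 names no step that separates PSB's share.

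Section 13 is the only analysis plan in the documents. Followed as written, a significant Time effect would be taken as supported efficacy, and Section V already says what would be concluded from that. The same result is compatible with no effect of PSB on any outcome. More subjects or better conduct would not cure this.

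**Working it through.** **1. What the test can identify.** Write the mean pre-to-post change as D = T + B, where T is the effect of PSB and B is all other change. With everyone treated, only D can be estimated. The Time test asks whether D is zero. If T = 0 and B is not zero, it can reject. If T is a benefit and B runs the other way, it can fail to reject. This follows from the design and needs no figures.

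**2. What could make B differ from zero, from the documents.**
- *Regression to the mean.* The Aim recruits "in individuals with either risky drinking problems or with high stress", and Section I, 8 lists both drinking and stress criteria. Stress and alcohol use are also outcomes. The extent is unknown: the heavy-drinking criterion is a past-year level, the binge criterion has no frequency, no Perceived Stress Scale cut is given, and craving is not an entry criterion.
- *Reactivity to measurement.* Baseline takes 4-5 assessment sessions (Section I, 4(a)), and daily surveys run through the 30-day follow-up. In weeks 1-4, self-monitoring and app use are partly ingredients of PSB (Section I, 2 and 4(b)). Reactivity is clearly separate from PSB only for the research assessments and the follow-up surveys.
- *Secular change.* Section I, 3 reports a pandemic-era rise in distress and alcohol misuse. Its course during the study is unknown. A continuing rise would mask benefit; a decline would mimic it.

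**3. The daily app measures.** Daily surveys are scheduled for the 28 intervention days and the 30 follow-up days (Section I, 2; Section VI). None is scheduled before PSB starts. The Timeline Follow-Back in Section I, 4(a) covers the previous ninety days, so it supplies pre-PSB drinking data. It is a different instrument, does not cover daily stress or mood, and is not a comparator.

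**4. Illustration.** The documents give no alpha, effect size, SD or dropout, so there is no figure of theirs to reproduce. Input from the documents: n = 100. Assumptions: two-sided 5%, normal outcome, zero PSB effect, and a non-treatment change of d SD of the pre-post differences. A paired t test has 99 degrees of freedom and noncentrality d x sqrt(100) = 10d.

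| d | Noncentrality | Chance of significance |
|---|---|---|
| 0.1 | 1.0 | 16.8% |
| 0.2 | 2.0 | 50.8% |
| 0.3 | 3.0 | 84.4% |

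If 80 were analysed (assumed), the last two become 42.4% and 75.5%. For the planned three-level Time test, with equal variances and correlations and the shift held at follow-up, d = 0.2 gives about 52% and d = 0.3 gives 87% to 88%.

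In baseline SD units the shift is d x sqrt(2(1 - r)). For an assumed retest correlation r of 0.9 to 0.6, d = 0.2 is 0.09 to 0.18 and d = 0.3 is 0.13 to 0.27. The percentages count significance in either direction. Only a shift towards improvement would be read as efficacy.

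**5. Is there a second group?** Section VI mentions assessment and intervention groups, Section I, 4 mentions the intervention group, and Section I, 13 mentions group differences. None defines membership, assignment or schedule. The payments for the intervention group add up as follows:
- sessions 160 + 40 = 200
- app 84 + 84 + 4 x 20 = 248
- four-week period, with the post assessment, 200 + 248 + 40 = 488
- follow-up 90 + 40 + 60 = 190
- total 100 + 488 + 190 = $778

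That equals the stated maximum per participant. A maximum equal to the intervention-group total fits one group, but a two-group study could show the same.

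**The case against.** The strongest reply is that a single-arm pre-post study is legitimate, that the Aim openly says before and after, and that Section V is conditional and calls PSB a potential programme. On this view the point limits interpretation and does not make the model wrong. Much of that stands: the Time model is a reasonable way to describe change, and no control arm is demanded here. But stating the contrast does not license the word efficacy, and Section V attaches a firm conclusion to it.

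Several stronger readings are tempting and are not supported:
- *Regression to the mean certainly inflates the result.* The entry cuts and retest correlations needed to show this are not given. It is possible, to an unknown extent.
- *All self-monitoring is a rival cause.* In weeks 1-4 it is partly PSB itself.
- *There are no pre-PSB drinking data.* The Timeline Follow-Back provides some.
- *The assessment group is merely stray wording, or is an untreated control.* Section I, 4(b) and the Aim favour a single arm, but the payment figures do not settle it. Only the investigators can.
- *PSB does not work.* Nothing here bears on that.

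**Conclusion.** The concern holds and should be corrected before results are interpreted. The test in Section 13 cannot support the efficacy conclusion the documents attach to it, whatever the data show. This rests on three facts in the text: PSB for all subjects, Time as the tested effect, and no defined comparator.

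The size and direction of any bias cannot be known from the documents. The figures of 17%, 51% and 84% show only how readily modest non-treatment change would reach significance with 100 subjects; the shifts of 0.1, 0.2 and 0.3 SD of the differences are assumptions. The conclusion does not depend on them. The inconsistent group wording is a separate matter to reconcile and adds nothing to the seriousness of the main point.

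**What to change.** In Section I, 13:
- Replace "To test the efficacy of the PSB intervention in reducing stress, alcohol craving and use" with *To estimate within-person change in stress, alcohol craving and use from pre to post and follow-up, with 95% confidence intervals*.
- In the sentence containing "will be used to evaluate the effects of prevention on prospective repeated assessments of stress", have the models *describe change over time in* those assessments instead of evaluating effects of prevention.
- Add: *Without a comparator, change over Time is not attributed to PSB.*

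Align the efficacy or effect wording in Section I, 1 (purpose, Aim and 30-day follow-up) and at the end of Section I, 3. Reword Section V so that improvement over time is said to support testing PSB against a comparator, not to identify an effective strategy.

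Separately, the investigators should confirm whether an assessment group exists, and reconcile Section I, 4 and 13 and Section VI with Section I, 4(b). If there is none, remove the group wording, or name the subgroups meant by group differences (for example heavy versus binge drinkers, or risky drinkers versus high-stress subjects). If a concurrent untreated group does exist, the rewording above is not the right repair: describe how that group is formed and test Group x Time instead.

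For a single-arm study, the model, sample, visits and data stay the same. The work is rewording across several sections, and the cost is a narrower conclusion, with no efficacy claim from this study.
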